8.1.2.1.1 Full Physical Exam

The Investigator or qualified designee will perform a complete physical exam during the screening period. Clinically significant abnormal findings should be recorded as medical history. A full physical exam should be performed during screening and at Day 1, at Cycle 4 and Cycle 8, and Day 1 at every fourth cycle onwards during study treatment as well as at the 30 days safety follow-up visit.

8.1.2.1.2 Directed Physical Exam

For cycles that do not require a full physical exam per the Trial Flow Chart, the Investigator or qualified designee will perform a directed physical exam as clinically indicated prior to trial treatment administration.

8.1.2.1.3 Vital Signs

The Investigator or qualified designee will take vital signs at screening, prior to the administration of each dose of trial treatment and at treatment discontinuation as specified in the Trial Flow Chart (Section 6.0). Vital signs should include temperature, pulse, oxygen saturation, weight and blood pressure. Height will be measured at screening only.

8.1.2.1.4 Eastern Cooperative Oncology Group (ECOG) Performance Scale

The Investigator or qualified designee will assess ECOG status at screening, prior to the administration of each dose of trial treatment, at discontinuation of trial treatment and during follow-up as specified in the Trial Flow Chart.

8.1.2.2 Tumor Imaging and Assessment of Disease

The imaging assessments will be performed by 18F-FDG PET/CT. The tumor response will be assessed according to RECIST v1.1 as primary method and by Immune Modified Response Evaluation Criteria in Solid Tumors (imRECIST) as secondary method. After baseline tumor assessments, evaluation of tumor response will be performed at Cycle 7, Day 1 (\pm 7 days), Cycle 16, Day 1 (\pm 7 days), at 12 months (\pm 10 days) from the date of first dose, and every 12 months thereafter (\pm 21 days) until 5 years after the first dose. Additional 18F-FDG PET/CT scans or other radiological evaluations will be performed if indicated.

8.1.2.3 Tumor Tissue Collection and Correlative Studies Blood Sampling

Fresh frozen and FFPE tumor biopsies will be obtained before start of treatment with nivolumab (Cycle 1), and thereafter optional before start of Cycle 2 (start of radiotherapy), at start of Cycle 3, and at disease relapse/progression.

PBMCs will be collected before start of treatment with nivolumab, and at Day 1 at the following cycles; Cycle 2, Cycle 3, Cycle 5, Cycle 9, Cycle 16 and at disease progression. Plasma and serum will be collected at baseline, Cycle 2 (Day 1 and 8), Cycle 3 (Day 1 and 8), Cycle 4 (Day 1), Cycle 5 (Day 1), Cycle 9 (Day 1), Cycle 16 (Day 1), Month 12 and at disease progression. For patients not progressing on study treatment, PBMCs and plasma and serum will also be collected 12 weeks after end of nivolumab therapy.

8.1.2.4 Laboratory tests

Laboratory tests for hematology, chemistry, urin analysis and other relevant tests are specified in Table 2. The lab results must be reviewed by the Investigator or qualified designee and found to be acceptable prior to each dose of trial treatment.

Table 2 Laboratory Tests

Hematology	Chemistry	Urine analysis	Other
Hematocrit	Albumin	Blood	Serum β -human chorionic gonadotropin†
Hemoglobin	Alkaline phosphatase	Glucose	
Platelet count	Alanine aminotransferase (ALT)	Protein	INR
WBC (total and differential)	Aspartate aminotransferase (AST)		aPTT
Red Blood Cell Count	Lactate dehydrogenase (LDH)	Microscopic exam if abnormal results are noted	
Absolute Neutrophil Count	Total protein		Free tyroxine (T4)
Absolute Lymphocyte Count	CRP	Urine pregnancy test †	Thyroid stimulating hormone (TSH)
	Creatinine		TPO
	Uric Acid		
	Calcium		
	Chloride		Amylase
	Glucose		Lipase
	Phosphorus		HBV sAg and HCV Ab or HCV RNA
	Potassium		HIV-test
	Sodium		
	Magnesium		PBMC
	Total Bilirubin		Plasma, serum
	Direct Bilirubin (If total bilirubin is elevated)		

† Perform on women of childbearing potential only.

8.1.2.5 Thyroid Function Testing

At Screening, thyroid function testing is to include TSH and free T4. At subsequent time points, thyroid function testing consists of TSH only. However, if the TSH is abnormal testing of free T4 is to be performed.

Management algorithms for suspected endocrinopathy adverse events (including abnormal thyroid function) can be found in the nivolumab investigator brochure.

8.1.3 Other Procedures

8.1.3.1 Withdrawal/Discontinuation

When a subject discontinues/withdraws prior to trial completion, all applicable activities scheduled for the final trial visit should be performed at the time of discontinuation. Any adverse events which are present at the time of discontinuation/withdrawal should be followed in accordance with the safety requirements outlined in Section 8.

8.1.3.2 Screening Period

Approximately 28 days prior to subject allocation, potential subjects will be evaluated to determine that they fulfill the entry requirements as set forth in Section 5.1. Visit requirements are outlined in Section 6.0 – Trial Flow Chart. Results of a test performed prior to the subject signing consent as part of routine clinical management are acceptable in lieu of a screening test if performed within the specified time frame. Screening procedures are to be completed within 28 days prior to the first dose trial treatment except for the following:

- Laboratory tests and ECOG PS are to be performed within 14 days prior to the first dose of trial treatment.
- For women of childbearing potential, a serum pregnancy test will be performed within 72 hours prior to the first dose of trial treatment. A urine test may be considered if serum test is not appropriate.
- The baseline tumor biopsy has to be obtained within 28 days prior to the first dose.

Subjects may be rescreened after initially failing to meet the inclusion/exclusion criteria. Results from assessments performed during the initial screening period are acceptable in lieu of a repeat screening test if performed within the specified time frame and the inclusion/exclusion criteria is met.

8.1.3.3 Treatment Period

Visit requirements are outlined in Section 6.0 – Trial Flow Chart. Specific procedure-related details are provided above in Section 7.1 – Trial Procedures.

8.1.3.4 Post-Treatment Visits

8.1.3.4.1 Safety Follow-Up Visit

The mandatory Safety Follow-Up Visit should be conducted approximately 30 days after the last dose of trial treatment or before the initiation of a new anti-cancer treatment, whichever comes first. All AEs that occur prior to the Safety Follow-Up Visit should be recorded. Subjects with an AE of Grade > 1 will be followed until the resolution of the AE to Grade 0-1 or stabilization, until the beginning of a new anti-neoplastic therapy, whichever occurs first. SAEs that occur within 90 days of the end of treatment or before initiation of a new anti-cancer treatment should also be followed and recorded.

8.1.3.4.2 Follow-up Visits

Subjects who discontinue trial treatment for a reason other than disease progression will move into the Follow-Up Phase. The remaining patients will move into the FollowUp Phase after end of nivolumab treatment. The patients should be assessed every 3 months the first year after discontinuation (± 7 days), the following three years (year 2-4 after discontinuation of study treatment) every six month, to monitor disease status. Every effort should be made to collect information regarding disease status until the start of new anti-neoplastic therapy, disease progression, death and end of the study. Information regarding post-study anti-neoplastic treatment will be collected if new treatment is initiated.

8.1.3.4.3 Survival Follow-up

Once a subject experiences confirmed disease progression or starts a new anti-cancer therapy, the subject moves into the survival follow-up phase. We will then monitor survival status by contacting the GP/local hospital or by phoning the patient every 3 month, until the end of the study. The survival status and, if applicable, the cause of death, will be recorded.

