5.5 Subject Withdrawal/Discontinuation Criteria

Subjects may withdraw consent at any time for any reason or be dropped from the trial at the discretion of the Investigator should any untoward effect occur. In addition, a subject may be withdrawn by the Investigator or the Sponsor if enrollment into the trial is inappropriate, the trial plan is violated, or for administrative and/or other safety reasons. Specific details regarding discontinuation or withdrawal are provided in Section 7.1.3 – Other Procedures.

A subject must be discontinued from the trial for any of the following reasons:

- AE as described above (section 5.3.2.3).
- The subject or legal representative (such as a parent or legal guardian) withdraws consent.
- Confirmed radiographic disease progression

Note: A subject may be granted an exception to continue on treatment with confirmed radiographic progression if clinically stable or clinically improved, please see Section 5.3.2.4

- Any clinical adverse event (AE), laboratory abnormality or intercurrent illness which, in the opinion of the investigator, indicates that continued participation in the study is not in the best interest of the subject
- Intercurrent illness that prevents further administration of treatment
- Investigator's decision to withdraw the subject
- The subject has a confirmed positive serum pregnancy test
- Noncompliance with trial treatment or procedure requirements
- The subject is lost to follow-up

- Administrative reasons

The End of Treatment visit procedures are listed in Section 6 (Protocol Flow Chart) and Section 7. After the end of treatment, each subject will be followed for 30 days for adverse event monitoring. Subjects who discontinue for reasons other than progressive disease will have post-treatment follow-up for disease status until disease progression, starting a non-study cancer treatment, withdrawing consent or becoming lost to follow-up. After documented disease progression, information on survival will be obtained until death, withdrawal of consent, or the end of the study, whichever occurs first.

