- h. Coagulation factors (PT/INR and aPTT) should be tested as part of the screening procedures for all subjects. Any subject receiving anticoagulant therapy should have coagulation factors monitored closely throughout the trial.
- i. Unresolved abnormal lab values that are drug related AEs should be followed until resolution. Lab tests do not need to be repeated after the end of treatment if lab tests are within normal range.
- j. Tumor assessments by 18F-FDG PET/CT will be performed at screening, (Cycle 7), (Cycle 16) and at Month 12 (± 1 week). Tumor response will be evaluated using both and RECIST v1.1 (Appendix 15.3) and immune-modified RECIST criteria (Appendix 15.4). In the absence of disease progression, tumor assessments should continue regardless of whether patients discontinue study treatment, unless they withdraw consent or the study is terminated by the Sponsor, whichever occurs first.
- k. Cycle 7 and Cycle 16, Month 12 and yearly thereafter until 5 years after start of treatment
- l. For patients not progressed during treatment, urine analysis, plasma and serum, and PBMC collection to be performed at first FU visit only (12 weeks after discontinuation).
- m. In subjects who discontinue study therapy, a radiologic evaluation should be performed at the time of treatment discontinuation (i.e., date of discontinuation ± 4 weeks). If a previous scan was obtained within 4 weeks prior to the date of discontinuation, then a scan at treatment discontinuation is not mandatory.
- n. Fresh frozen and FFPE tumor biopsies before start of treatment (Cycle 1), before start of radiotherapy (Cycle 2), at Cycle 3 and at disease relapse/progression.
- o. PBMC; at screening (or day 1 Cycle 1), and at Day 1 at the following cycles; Cycle 2, Cycle 3, Cycle 5, Cycle 9, Cycle 16 and at disease progression. 100 ml ACD blood at baseline. 50 ml ACD blood at later time points. To be taken before infusion of IMP. Plasma and serum will be collected at screening (or day 1 Cycle 1), Cycle 2 (Day 1 and 8), Cycle 3 (Day 1 and 8), Cycle 4 (Day 1), Cycle 5 (Day 1), Cycle 9 (Day 1), Cycle 16 (Day 1), Month 12 and at disease progression.
- p. Thyroid function testing is to be done every 6 weeks during nivolumab treatment.
- r. The sample collection is optional

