8.1.1.5.3 Subsequent Anti-Cancer Therapy Status

The Investigator or qualified designee will review all new anti-neoplastic therapy initiated after the last dose of trial treatment. If a subject initiates a new anti-cancer therapy within 30 days after the last dose of trial treatment, the 30 day Safety Follow-up visit must occur before the first dose of the new therapy. Once new anti-cancer therapy has been initiated the subject will move into survival follow-up.

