11.0 STATISTICAL ANALYSIS PLAN

11.1 Statistical Analysis Plan Summary

In this exploratory phase I study no formal hypothesis testing will be performed. Hence, the primary endpoint and secondary endpoints will be evaluated only by descriptive methods. Data will be described with proportions (percentage) for categorical data and with median, mean and range for continuous data. Kaplan-Meier curves will be produced for PFS and OS.

Progression free survival (PFS), defined as the time from inclusion to the occurrence of disease progression, as determined by investigators from tumor assessments per RECIST, or death from any cause, whichever occurs first. Data for patients without disease progression or death will be censored at the last tumor assessment date.

Overall survival (OS) will be calculated from the date of first dose of nivolumab until death. Patients alive at the time of data analysis will be treated as censored.

Exploratory analyses will be carried out to evaluate the data of the immunological and molecular analyses (e.g. biomarker studies) carried out. The statistical analyses will be dependent on the biological factors investigated and the analysis methodology used, and will be defined separately for each molecular study. With regard to some of the secondary/exploratory objectives, comparative analyses between groups or between samples obtained at different time points will be performed.

A number of 20 patients is considered suitable for addressing the primary endpoints, i.e. evaluating the safety and dose in the selected patient population. The biobank material obtained at consecutive time points from 20 patients should be sufficient for informative collateral studies.

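### The protocol contradicts itself on tumour assessment after new anti-cancer therapy, and if assessment stops there the SAP's PFS rule lets deaths after month 12 change the 12-month estimate

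*Combined protocol and SAP*

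**What the plan says.** Four sections close disease assessment when another anti-cancer treatment begins.

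- Section 5.5: patients who stop for reasons other than progression "will have post-treatment follow-up for disease status until disease progression, starting a non-study cancer treatment, withdrawing consent or becoming lost to follow-up".
- Section 8.1.1.5.3: "Once new anti-cancer therapy has been initiated the subject will move into survival follow-up".
- Section 8.1.3.4.2: sites are to make every effort to "collect information regarding disease status until the start of new anti-neoplastic therapy, disease progression, death and end of the study".
- Section 8.1.3.4.3: "Once a subject experiences confirmed disease progression or starts a new anti-cancer therapy, the subject moves into the survival follow-up phase". Contact in that phase is three-monthly, through the GP or local hospital or by telephone, and what it yields is limited: "The survival status and, if applicable, the cause of death, will be recorded".

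Three places say otherwise. Footnote j of the Trial Flowchart (7.0) reads "In the absence of disease progression, tumor assessments should continue regardless of whether patients discontinue study treatment, unless they withdraw consent"; the only other exception it names is termination of the study. Footnote k and Section 8.1.2.2 schedule PET/CT at Cycle 7, Cycle 16 and month 12, then yearly to 5 years, with no stop at new therapy.

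Section 11.1 counts RECIST progression or death from any cause as the PFS event. For everyone else: "Data for patients without disease progression or death will be censored at the last tumor assessment date". It has no rule for new therapy or for missed scans, and no PFS data cut-off date. Section 6.2 also counts any death during the study.

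**The concern.** PFS after 12 months is the first secondary objective (Section 4.1). Two investigators could each follow the protocol and collect different data on the same kind of patient: one keeps scanning after a switch, the other only telephones.

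Under the stopping rule, a patient who switches without RECIST progression can no longer have a progression recorded. The SAP then handles that patient according to later fate. One who dies stays at risk until the death date. One who survives is removed back at the last scan before the switch. Kaplan-Meier estimation needs censoring that does not depend on later outcome, and this rule breaks that condition. With 20 patients, each is worth 1/20 = 5 points of 12-month PFS, so a few switches are enough to matter.

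**Working it through.** The plan states no PFS figure, assumed switching rate or sample-size calculation, so there is nothing of its own to reproduce. The check has three steps.

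**1. Worked example, 20 patients (illustrative counts).** Day 1 of Cycle 7 is week 12 (6 × 2 weeks) and day 1 of Cycle 16 is week 30 (15 × 2 weeks). Suppose 2 events at week 12, 4 at week 30 and 2 at month 12, 8 patients event-free beyond month 12, and 4 who start new therapy at month 5 with no scan after week 12.

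All four alive at cut-off, so all censored at week 12:

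18/20 × 10/14 × 8/10 = 0.514.

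If k of the four die at month 18, those k remain at risk through month 12:

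0.9 × (10+k)/(14+k) × (8+k)/(10+k) = 0.9 × (8+k)/(14+k).

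| Deaths at month 18 (k) | 12-month PFS |
|---|---|
| 0 | 51.4% |
| 1 | 54.0% |
| 2 | 56.2% |
| 3 | 58.2% |
| 4 | 60.0% |

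More deaths after month 12 give a higher 12-month PFS. If all four die at month 9 instead, the result is 0.9 × 14/18 × 10/14 × 8/10 = 40.0%.

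With scans continued, if m of the four have progressed by month 12, PFS is (12 - m)/20: 60, 55, 50, 45 or 40% for m = 0 to 4. Deaths after month 12 then have no influence.

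**2. Direction and size (simulation, 400,000 patients per scenario).** These assumptions are not in the documents: median time to progression 6 to 12 months; median time to death 30 to 60 months before progression and 6 to 24 months after it; 10 to 30% starting new therapy by month 12; progression hazard after new therapy multiplied by 0.5, 1 or 3; 18-month uniform accrual; cut-off 0.5 to 60 months after the last patient enters. The reference is scans continued as in footnote j.

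One middle scenario (medians 9, 40 and 18 months; 20% switching by month 12). The first two result columns are 12-month PFS in %; the last three are differences in points:

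| Hazard multiplier | Cut-off (months) | Scans continue | Scans stop, SAP rule | Missed progressions | Back-censoring | Net |
|---|---|---|---|---|---|---|
| 0.5 | 0.5 | 32.3 | 29.5 | +4.0 | -6.8 | -2.8 |
| 0.5 | 60 | 34.0 | 36.7 | +3.8 | -1.0 | +2.7 |
| 1 | 0.5 | 30.3 | 29.2 | +5.7 | -6.7 | -1.1 |
| 1 | 60 | 32.2 | 36.8 | +5.4 | -0.8 | +4.6 |
| 3 | 0.5 | 27.1 | 29.3 | +8.5 | -6.3 | +2.1 |
| 3 | 60 | 28.5 | 36.4 | +8.6 | -0.7 | +7.9 |

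(Components may differ from the net by 0.1 through rounding.)

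Net difference across all scenarios:

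- Multiplier 1 or 3: +2.0 to +12.0 points at a 60-month cut-off, about 0 to +6.2 at 12 months, and -2.4 to +3.1 at 0.5 months.
- Multiplier 0.5: +1.7 to +2.9 at 60 months, and -0.4 to -3.0 at 12 months or less.

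At 20% switching, missed progressions added 3.0 to 8.8 points and back-censoring removed 0 to 6.8.

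**3. The discontinuation scan.** Footnote m asks for a radiologic evaluation within 4 weeks of stopping study therapy, unless one was done in the 4 weeks before. Step 2 leaves it out. Placing a scan at the switch lowered the upward error at a 5-year cut-off by about a quarter, without removing it. At a cut-off 30 weeks after the last patient, the error was slightly negative.

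**The case against.** A reader might infer that the plan as written simply inflates 12-month PFS, and that outcome-dependent censoring is the cause. The documents support neither. They fix no PFS cut-off, and the sign depends on it. Censoring survivors back at the last scan lowers the estimate; the upward push comes from progressions nobody sees.

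A reader might also infer that scans are expressly ordered to stop. The four sections speak of disease status or a change of follow-up phase and do not name scans. That assessment ends is a reasonable inference, because survival follow-up records only vital status and cause of death, but it remains an inference. Footnote j, for its part, speaks of stopping study treatment and does not mention new therapy.

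It is also fair to say that the stakes are modest. No hypothesis is tested, and the primary objectives concern safety and dose. At a PFS near 25% the standard error is √(0.25 × 0.75/20) ≈ 9.7 points, so an error of 1 or 2 points would be lost in the noise. The documents give no basis for a high rate of switching without RECIST progression.

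The contradiction still stands, as does the dependence of a month-12 estimate on later deaths, which needs no assumption about hazards. Late analysis is also the more likely course: no interim efficacy analysis is planned (Section 3.0), the study ends 5 years after the last inclusion (8.2), and results are submitted on completion (13.6). Those are the conditions under which every simulated scenario erred upward.

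**Conclusion.** The concern holds in this form. Four sections conflict with footnotes j and k and with Section 8.1.2.2, and Section 11.1 does not resolve the conflict. If assessment stops at new therapy, the literal PFS rule lets later deaths move the 12-month figure, by 8.6 points (60.0 - 51.4) in the worked example.

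The net error is about +2 to +12 points with mature follow-up. It can be near zero, or about -3 points, at an early cut-off or, short of mature follow-up, if new therapy slows progression. The footnote m scan reduces the upward error. All simulated sizes rest on assumed switching, progression and survival rates. The endpoint is descriptive and secondary, so this is a correction that should be made; it does not threaten the design.

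**What to change.** 1. Reconcile Sections 5.5, 8.1.1.5.3, 8.1.3.4.2 and 8.1.3.4.3 with footnotes j and k and Section 8.1.2.2, so that tumour assessments already on the schedule continue to RECIST progression after new therapy starts. Section 8.1.3.4.2 must be included, or the conflict survives.
2. State in Section 11.1 that progression or death counts as a PFS event regardless of new therapy, and fix the PFS data cut-off.
3. Add a sensitivity analysis that censors every patient who switches at the last assessment before new therapy, whatever happens afterwards. This also removes the dependence on later deaths. It may be optimistic if switching is linked to prognosis: in the simulation it lay within 1 point of the scans-continued result when new therapy left the progression hazard unchanged, but 1 to 5 points above it when that hazard tripled. Counting new therapy as an event would be a useful companion analysis.

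The cost is protocol and SAP wording, plus a few already scheduled scans in patients who switch.
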